6.5.4 Electrocardiograms

ECG variables will be summarized using mean, standard deviation, median, minimum, and maximum, for each age group and overall, by treatment group and visit, including changes from baseline. Summary of ECG data will be presented for visits 1, 3, 5, 7, and for EoT values.

Number and percent of subjects with normal, not clinically significant abnormal, and clinically significant abnormal results as assessed by investigator for the 12 lead ECG will be tabulated, for each age group and overall, by treatment group and visit.

Shift tables will be presented for changes from baseline at each visit including local interpretation categories. Shift tables will also be presented as above from baseline to worst post-baseline value during the treatment period.

The corrected QT interval (i.e. QTcF) will be summarized for each visit showing the number and percentage of subjects in each of the following categories:

For the children category:

• 440 ms

For the male adolescents category:

- 450 ms
- 500 ms

For the female adolescents category:

- 480 ms
- 500 ms

Note that these categories are cumulative in that subjects satisfying criterion for more extreme category will also be counted in each applicable less extreme category.

The corrected QT interval (i.e., QTcF) will also be summarized, for each age group and overall, by treatment group and visit showing the frequencies of subjects with the following changes from baseline: <0, ≥ 0 and <30, ≥ 30 and <60, and ≥ 60 ms.

Number and percent of subjects with 12 lead ECG abnormalities as well as number and percent of subjects whose 12 lead ECG reading changed from normal at baseline to abnormal will be tabulated, for each age group and overall, by treatment group and visit.

ECG data will be provided in listing format by country, site and subject for the SAF.

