Abbreviations	Description of abbreviations
PD1-x	Protocol Deviation 1-x
РК	Pharmacokinetic
PKAS	Pharmacokinetics Analysis Set
PKDAP	Pharmacokinetic Data Analysis Plan
PPIUS	Patient Perception of Intensity of Urgency Scale
PPS	Per-Protocol Set
РТ	Preferred Term
PVR	Post Void Residual
QTc	Corrected Q-T Interval
QTcF	QT interval corrected by Fridericia's formula
SAF	Safety Analysis Set
SAP	Statistical Analysis Plan
SAS	Statistical Analysis Software
SBP	Systolic Blood Pressure
SOC	System Organ Class
TEAE	Treatment Emergent Adverse Event
TLF	Tables, Listings and Figures
UA	Urinalysis
ULN	Upper Limit of Normal
UTI	Urinary Tract Infection
WHO-DD	World Health Organization Drug Dictionary

List of Key Terms

Terms	Definition of terms				
Baseline	Observed values/findings which are considered to be the starting point for				
Discontinuation	The act of concluding participation in a trial by an enrolled subject, prior to completion of all protocol required elements. Note: subject discontinuation does not necessarily imply exclusion of subject data from analysis that was collected prior to discontinuation				
Enroll	To register or enter into a clinical trial, i.e., signing the informed consent form (ICF). Once a subject has been enrolled, the clinical trial protocol applies to the subject.				
EoT result	End of treatment result is based on the last available result which is obtained earlier or on the same date as the treatment stop date.				
Investigational period Pediatric	Period of time where major interests of protocol objectives are observed, and where the study drug is given to a subject. This period continues until the last assessment after completing the last dose of the study drug. Weight-range based doses predicted to achieve plasma concentrations				
equivalent dose (PEDx)	equivalent to steady state exposures expected with "x" mg mirabegron administered once daily in adults.				
Postinvestigational period	Period of time after the last assessment of the protocol. Follow-up observations for sustained adverse events and/or survival are done in this period.				
Screening	A process of active consideration of potential subjects for a trial.				
Screening period	Period of time before entering the investigational period, usually from the time the subject signed informed consent until just before the first dose of the study drug is given to a subject.				

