6.10 Additional Conventions

6.10.1 Analysis Windows

The study protocol gives the overall study schedule and the permissible intervals for these visits expressed as the number of days relative to visit 3/baseline. The total time each subject will be in the study will not exceed 18 weeks with a maximum of a screening period of 4 weeks and a maximum of 14 weeks for the investigational period.

Analyses will not exclude subject data due to the subject's failure to comply with the visit schedule.

Visit Windows for Efficacy and Safety Parameters

CRF visit	Target day relative to Baseline (Visit 3, Day -1)	Analysis Window	Analysis visit
Bladder e-d	liary		
Visit 3	Last value prior to first dose	Day -7 to Day 1 (prior to first dose)	Baseline
Visit 4	Day 14	Day 7 to Day 21	Week 2
Visit 5	Day 28	Day 22 to Day 42	Week 4
Visit 6	Day 56	Day 43 to Day 70	Week 8
Visit 7	Day 84	Day 71 to Day 91	Week 12
ЕоТ	Day 84	Day 1 to \leq Last dose of double- blind study drug	ЕоТ
Acceptabili	ty questionnaires		
Visit 7	Day 84	Day 71 to Day 91	Week 12
ЕоТ	Day 84	Day 1 to \leq Last dose of double- blind study drug	ЕоТ
SBPM			
Visit 3	Last value prior to first dose	Day -7 to Day 1 (prior to first dose)	Baseline
Visit 4	Day 14	Day 7 to Day 21	Week 2
Visit 5	Day 28	Day 22 to Day 42	Week 4
Visit 6	Day 56	Day 43 to Day 70	Week 8
Visit 7	Day 84	Day 71 to Day 91	Week 12
ЕоТ	Day 84	Day 1 to \leq Last dose of double- blind study drug	ЕоТ
Table contin	nued on next page		

All the assessments will be allocated to CRF visit based on Table 10.

CRF visit	Target day relative to Baseline (Visit 3, Day -1)	Analysis Window	Analysis visit	
Vital signs				
Visit 1			Screening	
Visit 3	Last value prior to first dose	Day -7 to Day 1 (prior to first dose)	Baseline	
Visit 5	Day 28	Day 22 to Day 56	Week 4	
Visit 7	Day 84	Day 57 to Day 91	Week 12	
ЕоТ	Day 84	Day 1 to \leq Last dose of double- blind study drug	ЕоТ	
Visit 8 [#]	Day 98	Day 92 or EoT + 1 to no more than 17 days after EoT	Week 14 (EoS)	
ECG	-			
Visit 1			Screening	
Visit 3	Last value prior to first dose	Day -7 to Day 1 (prior to first dose)	Baseline	
Visit 5	Day 28	Day 22 to Day 56	Week 4	
Visit 7	Day 84	Day 57 to Day 91	Week 12	
ЕоТ	Day 84	Day 1 to \leq Last dose of double- blind study drug	ЕоТ	
Clinical Lab	ooratory Tests (Hematology, B	iochemistry and Urinalysis)		
Visit 1			Screening	
Visit 3	Last value prior to first dose	Day -7 to Day 1 (prior to first dose)	Baseline	
Visit 5	Day 28	Day 22 to Day 56	Week 4	

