Visit 7	Day 84	Day 57 to Day 91	Week 12	
ЕоТ	Day 84	Day 1 to \leq Last dose of double- blind study drug	ЕоТ	
Visit 8 [#]	Day 98	Day 92 or EoT to no more than 17 days after EoT	Week 14 (EoS)	
Post Void Residual (PVR) Volume				
Visit 3	Last value prior to first dose	Day -7 to Day 1 (prior to first dose)	Baseline	
Visit 5	Day 28	Day 22 to Day 56	Week 4	
Visit 7	Day 84	Day 57 to Day 91	Week 12	
ЕоТ	Day 84	Day 1 to \leq Last dose of double- blind study drug	ЕоТ	
Visit 8 [#]	Day 98	Day 92 or EoT to no more than 17 days after EoT	Week 14 (EoS)	

[#]Visit 8 may occur earlier due to early discontinuation as it is the last scheduled study visit.

For non-diary data, if a subject has more than one non-missing value within a visit window, the non-missing assessment which is closest to the target day within a window will be used. If two or more values are equally close and on different days, the latest non-missing value will be used. If two or more values are equally close and on the same day, the mean will be used for continuous variables or the worst observed case for categorical variables.

For diary data, the assessment date for the whole diary will be considered to be the date of the last valid day of the diary. If more than one diary has an assessment date within the same window, and if this results in more than one non-missing value of a diary variable, the non-missing value with the diary assessment day that is closest to the target day will be used. In case of ties on different days, the later non-missing value will be used. In case of ties located on the same side of the target day (i.e., more than one value for the same day), the mean of the values will be used for continuous variables and the worst value for categorical variables. For analyzing diary data the labels of the study visits will not be used, they will be assigned based on the dates of assessment.

A two-day window around the visit date will be applied for the assignment of study period for exposure data.

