6.10.2.3 Imputation Rules for Concomitant Medications

In case of missing partial start and stop dates for concomitant medications, the following rules will be used:

If the start date is missing or partial:

- if the month is missing, use January
- if the day is missing, use the first day of the month under consideration
- if the year is missing, use year of the informed consent date
- if the entire date is missing, use informed consent date

If the stop date is missing or partial:

- if the month is missing, use December
- if the day is missing, use the last day of the month under consideration
- if the year or the entire date is missing, set the stop date to December 31st, 2099

If the imputed start date is after the stop date, then the imputed start date will be 1 day prior to the stop date.

6.10.2.4 Imputation Rules for Missing Safety Variables (Lab values, Vital Signs, ECGs or PVR)

In case subject safety data of lab values, vital signs, PVR or ECGs at EoT (visit 7/week 12) is missing, the LOCF method will be used for the summaries or shifts from baseline to EoT only. No values at baseline and no data from more than 5 days after the last dose of study medication will be carried forward to post-baseline visits.

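### SAP 6.5.4 counts QTcF exceedances only by visit and EoT, so no table it describes gives, by arm, the subjects ever above threshold or ever ≥30 or ≥60 ms over baseline

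*SAP*

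**What the plan says.** SAP 6.5.4 gives two QTcF tabulations. For the first, "The corrected QT interval (i.e. QTcF) will be summarized for each visit showing the number and percentage of subjects" above 440 ms (children), 450 and 500 ms (male adolescents), or 480 and 500 ms (female adolescents). These categories are cumulative across severity, not across time. The second bands the change from baseline, with cuts at 0, 30 and 60 ms, by treatment group and visit. ECG summaries cover visits 1, 3, 5 and 7 and EoT, so the post-baseline rows are Week 4, Week 12 and EoT.

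Each visit row holds one value. Under SAP 6.10.1, "the non-missing assessment which is closest to the target day within a window will be used", with the later day taken on ties. The Week 4 ECG window in Table 10 is "Day 22 to Day 56" and the Week 12 window is Days 57 to 91.

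EoT is a last value, not a worst value, and it is described in three ways:
- The List of Key Terms uses "the last available result which is obtained earlier or on the same date as the treatment stop date".
- Table 10 uses Day 1 up to the last dose.
- SAP 6.10.2.4 carries values forward to EoT, but "no data from more than 5 days after the last dose of study medication will be carried forward to post-baseline visits".

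The one worst-value ECG output in 6.5.4 is a shift table: "Shift tables will also be presented as above from baseline to worst post-baseline value during the treatment period". The sentence it refers back to is "Shift tables will be presented for changes from baseline at each visit including local interpretation categories". Neither sentence names a QTcF cut-off.

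**The concern.** Protocol 2.1.3 lists QT prolongation as a potential risk, protocol 7.3.6 makes it an event of special interest, and protocol 8.1 makes QTcF above 440 ms, or a rise of more than 30 ms, a reason to stop treatment. The natural by-arm safety question is how many subjects ever reached those levels on drug and how many on placebo. Rows that each hold one selected ECG answer a different question: how many were above the cut-off at a nominal time.

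The SAP takes the other approach elsewhere. Liver tests use each subject's highest value in the investigational period (6.5.2.2), and post-void residual volume has a row for the maximum post-baseline value (6.5.6.1). QTcF has neither. At stake is an incomplete by-arm count of an outcome that should be rare, where one or two subjects can change how the arms compare.

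**Working it through.** The plan has no figure to reproduce. The check is to apply its selection rules to specific ECG sequences. All QTcF values below are assumed.

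**Inputs.** Week 4 window Days 22–56, target Day 28; Week 12 window Days 57–91, target Day 84; closest to target, later day on ties (SAP 6.10.1, Table 10). EoT as described above. Visit 5 allowed on Day 28 ± 3, that is Days 25–31 (protocol Table 1).

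**Condition for missing every row.** An ECG must lose its visit row and also not be the EoT value. It loses its visit row when another ECG in the window is nearer the target. An unscheduled ECG before Day 22 has no visit window at all.

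**Sequence A: unscheduled peak.** Day 28 = 420, Day 40 = 455, Day 42 = 425, Day 84 = 425.
- Distances from Day 28 are 0, 12 and 14 days, so Week 4 = 420.
- Week 12 = 425 (Day 84).
- EoT = 425, whether dosing ran to Day 84 or stopped with the Day 42 dose. In the latter case the off-treatment Day 84 ECG still fills the Week 12 row.
- The 455 is in no row. With an assumed baseline of 410, the peak change is 455 − 410 = 45 ms, while the rows show 10, 15 and 15 ms, all below the 30 ms band.
- Contrast: if the last dose is on Day 40, Table 10 gives EoT = 455 and the subject is counted there.

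**Sequence B: the ECG that prompts stopping.** Visit 5 on Day 26, predose ECG = 455, dose withheld, last dose Day 25, follow-up ECG on Day 29 = 425.
- Week 4: |26 − 28| = 2 and |29 − 28| = 1, so the row takes 425.
- EoT depends on the definition:

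| EoT read as | EoT value | 455 counted? |
|---|---|---|
| Up to last dose, Day 25 (Table 10) | none | no |
| Up to 5 days after last dose (6.10.2.4) | 425 | no |
| Up to treatment stop date, if that is Day 26 (Key Terms) | 455 | yes |

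Now let visit 5 fall on day s, the last dose on s − 1 and the follow-up ECG on day f > s. The visit row is lost when |f − 28| ≤ |s − 28|:
- s = 25: f = 26–31, 6 pairs
- s = 26: f = 27–30, 4 pairs
- s = 27: f = 28–29, 2 pairs
- s = 28 to 31: none

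That is 6 + 4 + 2 = 12 day-pairs under Table 10. Under 6.10.2.4 the follow-up must also fall by day s + 4, which removes s = 25 with f = 30 or 31 and leaves 10. If the stop date is the day of the ECG, none is missed.

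**What does not lose a value.** Day 28 = 455 with a Day 29 repeat of 425 still gives Week 4 = 455, because Day 28 is nearer the target. This holds whether or not the subject is withdrawn.

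**Visit rows without any lost ECG.** With a subjects above the cut-off at Week 4 and b at Week 12, the number ever above it among those values lies between max(a, b) and a + b. With assumed counts a = 2 and b = 3 in an arm of 92: 3 to 5 subjects, or 3/92 = 3.3% to 5/92 = 5.4%.

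**Same-day repeats.** SAP 6.10.1 says that for equally close values "on the same day, the mean will be used for continuous variables or the worst observed case for categorical variables". It does not say which rule applies to banded QTcF. With baseline 410 and same-day readings of 455 and 421, the mean is 438 (change 28, not counted) and the worst case is 455 (change 45, counted).

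**The case against.** The strongest reply is that the EoT row already does most of the job. If protocol 8.1 is followed, a subject above the limit at Week 4 stops and that ECG is normally the EoT value; for everyone else EoT is normally the Week 12 ECG. The EoT row is then close to an ever-count, near the upper end of the bound above. That stands, and it is why the point is small.

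Other by-arm outputs also help: disposition by primary reason (SAP 6.2.1), TEAEs leading to permanent discontinuation and the AEs of interest found by the QT query (5.4.1, 6.5.1), and PD2 for subjects not withdrawn (6.2.2). ECG data are listed by subject. These are real cover, but they count reasons, reported terms or deviations rather than measured QTcF in the SAP's bands.

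The worst-value shift table could be programmed with QTcF categories, since its wording is not exclusive and the TLF specifications are not among the documents. The SAP text assigns it none. It is also true that protocol 9.5.5 asks only for summaries by treatment group and visit, so the SAP complies with it.

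A reader might infer that the ECG that ends treatment is routinely dropped. The documents do not support that. ECG comes before the predose blood sample and is read in real time, so Sequence B is possible, but nothing says the dose waits for the reading. No ECG is scheduled on the following few days, and the loss disappears if EoT runs to a stop date equal to the ECG day. Nor does failure to withdraw, or a later lower repeat, remove a value by itself.

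**Conclusion.** The point holds as a missing tabulation. The QTcF bands are described only by visit and EoT, one value each, so no described table directly gives the by-arm count of subjects ever above threshold or ever at least 30 or 60 ms over baseline. A single exceedance escapes every row only under particular sequences: a better-placed ECG takes its visit row (or no window covers it) and a later on-treatment ECG supplies EoT; or the stop-prompting ECG falls after the last dose, a nearer follow-up takes the visit row, and EoT is read by last dose.

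The size cannot be estimated from the documents. It should be small, assuming protocol 8.1 is followed and few unscheduled ECGs are taken. It would be wrong to conclude that QT data are lost or that the safety assessment is invalid: the ECGs are collected and listed, and the unseen TLF specifications may already add detail. Minor.

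**What to change.** In SAP 6.5.4 add a maximum post-baseline QTcF row to the threshold table and a maximum change from baseline row to the change table, by age group and treatment. Take the maximum over all individual, unaveraged ECGs on treatment, scheduled and unscheduled, plus any ECG that prompts stopping even if it falls after the last dose. Keep the by-visit and EoT rows. Using individual readings also settles the same-day question for these rows. The cost is one extra row in each of two tables, from ECGs already collected.

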- 13. Subject has QTcF > 440 msec on screening ECG, a risk of QT prolongation (e.g., hypokalemia, long QT syndrome [LQTS] or family history of LQTS or exercise-induced syncope) or is currently taking medication known to prolong the QT interval.

- CONFIDENTIAL -

14. Subject's aspartate aminotransferase (AST) or alanine aminotransferase (ALT) is \geq 2 × upper limit of normal (ULN) or total bilirubin (TBL) is \geq 1.5 × ULN according to age and sex (subjects with Gilbert's syndrome are excepted from the bilirubin threshold).

ISN/Protocol: 178-CL-204

- 15. Subject has mild or moderate renal impairment (estimated glomerular filtration rate according to the modified Schwartz of < 60 mL/min per 1.73 m²).
- 16. Subject has a symptomatic (symptoms can include pain, fever, hematuria, new onset foul-smelling urine) UTI. Note: if the UTI is treated successfully (clinical recovery: confirmed by dipstick test and repeated dipstick test after 14 days [both should be negative]), the subject can be rescreened.
- 17. Subject has a history or presence of any malignancy.
- 18. Subject uses any drugs that are sensitive cytochrome P450 2D6 (CYP2D6) substrates with a narrow therapeutic index, sensitive P-glycoprotein (P-gp) substrates, or moderate or strong cytochrome CYP3A4/5 or P-gp inhibitors or inducers after the start of washout.
- 19. Subject is using or has used prohibited prior and/or concomitant medication(s) [Appendix 12.6 List of Excluded Concomitant Medications] that cannot be discontinued.
- 20. Subject has known or suspected hypersensitivity to mirabegron or any components of the formulations used.
- 21. Subject has participated in another clinical study (and/or subject has received any investigational therapy within 30 days (or 5 half-lives of the drug, or the limit set by national law, whichever is longer) prior to visit 1/week -4 (screening).
- 22. Subject received urinary catheterization within 2 weeks prior to screening.
- 23. Subject has constipation as defined by the Rome IV criteria that cannot be successfully treated prior to study entry.
- 24. Female subject who has been pregnant within 6 months prior to screening or breastfeeding within 3 months prior to screening.
- 25. Subject has any condition, which in the opinion of the investigator, makes the subject unsuitable for study participation.

Additional Exclusion at Visit 3/Week 0 (Baseline)

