8 DISCONTINUATION

8.1 Discontinuation of Individual Subject(s) From Study Treatment(s)

A discontinuation from treatment is defined as a subject who is randomized and for whom study treatment is permanently discontinued for any reason.

The subject is free to withdraw from the study treatment and/or study for any reason and at any time without giving reason for doing so and without penalty or prejudice. The investigator is also free to discontinue the participant from study treatment or to terminate a subject's involvement in the study at any time if the subject's clinical condition warrants it.

The reason for discontinuation from study treatment must be documented in the subject's medical records.

[‡] Volume does not take any unscheduled visits or repeat tests into account (e.g., follow up of adverse events).

Sponsor: APGD ISN/Protocol: 178-CL-204

A subject must discontinue study treatment for any of the following reasons:

- Subject requests to stop treatment.
- Any clinical AEs, laboratory abnormality or intercurrent illness, in the opinion of the investigator, indicates continued treatment is not in the best interest of the subject.
- If signs or symptoms of hypersensitivity to mirabegron are observed (e.g., anaphylactic reaction, erythema multiforme or exfoliative dermatitis).
- ALT or AST $> 8 \times ULN$.
- ALT or AST $> 5 \times ULN$ for more than 2 weeks.
- ALT or AST > $3 \times \text{ULN}$ and TBL > $2 \times \text{ULN}$ or international normalized ratio (INR) > 1.5 (if INR testing is applicable/evaluated).
- ALT or AST $> 3 \times$ ULN with the appearance of fatigue, nausea, vomiting, right upper quadrant pain or tenderness, fever, rash and/or eosinophilia (> 5%).
- Female subject becomes pregnant.
- Prolongation of QT > QTcF > 440 msec and/or QT interval prolongation > 30 msec versus baseline.
- Subject with (systolic blood pressure ≥ 160 mm Hg or diastolic blood pressure ≥ 100 mmHg.

If a subject discontinues treatment prematurely, the subject will be encouraged to complete all scheduled visits to record all available information.

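### The absolute-QTcF table in the SAP has no 440 ms row for adolescents, although the protocol applies QTcF > 440 msec at every age

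*SAP*

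**What the plan says.** Protocol 5.2, exclusion criterion 13, applies to all subjects aged 5 to < 18 years: "Subject has QTcF > 440 msec on screening ECG". Protocol 8.1 opens its list with "A subject must discontinue study treatment for any of the following reasons" and includes "Prolongation of QT > QTcF > 440 msec and/or QT interval prolongation > 30 msec versus baseline". The wording of that item is awkward, but its absolute limb reads as QTcF above 440 msec. Neither criterion has a separate value for adolescents or for either sex.

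SAP 6.5.4 summarizes QTcF at each visit as numbers and percentages of subjects, in three blocks:

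- "For the children category": 440 ms.
- "For the male adolescents category": 450 and 500 ms.
- "For the female adolescents category": 480 and 500 ms.

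A note makes the rows cumulative: "subjects satisfying criterion for more extreme category will also be counted in each applicable less extreme category". A second QTcF summary, "showing the frequencies of subjects with the following changes from baseline", uses the bands < 0, 0 to < 30, 30 to < 60 and ≥ 60 ms, by age group and overall. The same section provides means, maxima, investigator interpretations, shift tables and a listing by subject.

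**The concern.** QT prolongation is a named potential risk (Protocol 2.1.3) and part of an adverse event of special interest (Protocol 7.3.6). Because screening excludes anyone above 440 msec, crossing 440 msec on study is the protocol's own absolute signal. The safety table should let a reader see how often it occurred in each arm. For children it does. For adolescents it does not, and the SAP gives no reason for the difference.

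The practical effect is uneven. A child at 445 ms is counted. A boy at 445 ms or a girl at 470 ms meets the same stopping criterion but appears in no absolute-QTcF row.

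**Working it through.** No power, sample size or error-rate figure is involved. The check sets the protocol criterion beside the SAP cuts.

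**Width of the gap** (lowest SAP row minus protocol criterion)

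| Group | Protocol criterion | Lowest SAP row | Gap |
|---|---|---|---|
| Children, 5 to < 12 | > 440 msec | 440 ms | none |
| Male adolescents | > 440 msec | 450 ms | 450 − 440 = 10 ms |
| Female adolescents | > 440 msec | 480 ms | 480 − 440 = 40 ms |

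The SAP list as read carries no comparison signs. Reading the rows as > or as ≥ moves only the exact boundary values.

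**Does the cumulative note close the gap?** No. It carries a subject with a high value down into the lower listed rows. It does not bring in anyone below the lowest row.

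**Do the change bands close it?** Partly. Take a baseline B no higher than 440 ms and an on-study value V.

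- V is certain to fall in the ≥ 30 ms bands only when V ≥ 440 + 30 = 470 ms. So a girl from 470 to 480 ms appears there whatever her baseline.
- Below 470 ms it depends on B. A girl going from 425 to 445 ms has a change of 445 − 425 = 20 ms. She meets the absolute limb of the stopping criterion, enters no absolute row, and sits in the 0 to < 30 ms band beside unremarkable changes.
- In the male gap, V is at most 450 ms, so any boy with a baseline above 450 − 30 = 420 ms stays below the 30 ms band.
- Criterion 13 is checked at screening, and the baseline-visit exclusions in Protocol 5.2 have no QTcF limit. A baseline value could therefore itself exceed 440 ms, and the bands would then pick up less.

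**Do the other ECG outputs give the count?** The maximum by age group, arm and visit shows whether any adolescent exceeded 440 ms, but not how many. The listing holds each value, but a reader would have to count by hand.

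**Scale.** SAP 3 plans at least 32 adolescents, at least 16 on mirabegron. In an arm of 16, one adolescent is 1/16 = 6.25%, so even a single uncounted case would be visible as a percentage. The documents give no basis for estimating how many such cases will occur.

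**The case against.** The case against is substantial.

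- **Reporting categories need not equal stopping thresholds.** Protocol 9.5.5 promises only ECG summaries separately for children and adolescents and names no cut. This stands: the SAP breaks no rule in the protocol. The point is an improvement in reporting.
- **Much is already visible.** If the adolescent maximum is not above 440 ms, the missing count is zero. The change bands catch the upper part of the girls' gap. QT prolongation events are also searched with a broad query (SAP 5.4.1), and adverse events leading to discontinuation are tabulated. This stands too, but none of these outputs gives the number of adolescents above 440 ms by arm.
- **A later protocol may differ.** The SAP refers to a possible protocol version 3 (5.4.2.1, 5.4.6); the one reviewed is version 2.0. A later QTcF rule cannot be ruled out, though subjects treated under version 2.0 were subject to 440 msec.

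A reader might also infer more than the documents support:

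- *That every adolescent above 440 ms goes uncounted.* Boys beyond 450 ms and girls beyond 480 ms are counted.
- *That 32 adolescents are affected.* That is the planned minimum number randomized. Only those whose values fall in the gap are affected.
- *That a pooled count above 440 ms is impossible.* ECG values are listed by subject for the SAF, so the count can be made; it is simply not planned.
- *That a 440 ms row would reconcile with discontinuations or with deviation PD2.* It would not. The stopping rule has a second limb, a rise of more than 30 msec from baseline, and PD2 pools every withdrawal criterion.

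**Conclusion.** The point holds as a minor gap in the categorical summary. Adolescents above 440 and up to 450 ms (male) or up to 480 ms (female) meet a protocol exclusion and stopping value but enter no absolute-QTcF row, while children at the same values are counted. No data are lost, and the primary efficacy analysis is untouched.

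The conclusion assumes that the QT item in Protocol 8.1 means QTcF above 440 msec for all subjects, and that no protocol version not seen here changes that value. It does not depend on how many adolescents fall in the gap, which may be zero, and it takes no position on which QTcF threshold is clinically right.

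**What to change.** Keep the existing SAP 6.5.4 categories. Add one row giving the number and percentage of subjects with QTcF above the protocol's 440 msec criterion, for each age and sex group and overall, by treatment arm and visit. If the sponsor prefers the present adolescent categories alone, reconcile the two documents by stating in the SAP why they differ from the protocol criterion.

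The cost is one extra row in a planned table, from ECG data already collected. It needs no new assessment and can be settled before database hard lock.
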